satellite outpatient clinics in Canton, East Hartford, Putnam, Simsbury, Southington, Storrs, and West Hartford CT. Based on prior UConn ARC pharmacotherapy trials open to men and women (Kranzler, Tennen et al. 2009, Kranzler, Armeli et al. 2011, Kranzler, [name] et al. 2014) we anticipate that 35% of subjects will be female. Approximately 260 subjects will be enrolled (in person screening visit) with the goal of randomizing 190 to medication with 160 completing the initial 12 weeks of treatment. In the current study limited to men only, we enrolled 189 men and of these randomized 142. At least four factors will contribute to success in enhancing our recruitment in order to randomize 190 subjects in the proposed study: i) inclusion of women (35% of subjects), ii) UCONN Health has recently adopted the EPIC electronic medical record system which includes clinical trial notice pop up feature on clinicians' patient management screens with link to information about our clinical trial for patients with a clinic problem list entry of alcohol use disorder, iii) involvement of [name] as a co-investigator who is the past-president and current board member of the CT Chapter of the American Society for Addiction Medicine and has agreed to send an informational letter and recruitment flyers for the study to all central CT members of ASAM, and iv) the PI's greater experience in recruitment compared with the current study which was the first clinical trial for which he served as Principal Investigator.

2.C.2.a. Temporal Sequence of Screening: Prospective participants will first undergo phone screening including the AUDIT-C three-item screener (Dawson, Grant et al. 2005) to assess key inclusion / exclusion criteria. Patients who appear to be eligible will be invited for an in-person screening. After informed consent is obtained, staff will administer several questionnaires, obtain a medical history, collect urine and blood specimens for clinical screening and for genotyping the *FKBP5* rs1360780 polymorphism to allow balanced genotype distributions in the dutasteride and pbo treatment arms. Patients will receive a physical examination by a study physician and if no exclusions are identified will be randomized to receive study medication.

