2.C.3.a. Dutasteride is FDA approved to treat prostatic hypertrophy and is a competitive and specific inhibitor of both type I and type II steroid 5α-reductase enzymes with which it forms a stable enzyme complex with very slow dissociation. In humans, type I 5AR is present in the brain, liver, adrenal gland, and adipose tissue and is responsible for onethird of circulating DHT. Type II 5AR is present in the liver and prostate, and is responsible for two-thirds of circulating DHT. For studies of alcohol use, inhibition of type I 5AR may be of particular importance, as type I 5AR, but not type II enzyme, is present in the adult brain (Lephart, Lund et al. 2001) where local generation of neuroactive steroids is thought to occur in addition to peripherally generated neuroactive steroids. The dutasteride dose of 1 mg/day proposed for this study is expected to achieve a >90% inhibition of peripheral type II 5AR and a 60% inhibition of type 1 5AR by 4 weeks for a total reduction in DHT of ≅ 80% by 4 wks based on pharmacokinetic models (Gisleskog, Hermann et al. 1998) and consistent with our observed 80% reduction in 3α-adiol glucuronide at 6 wks in our recently completed initial study in men using this dose. Dutasteride will be purchased commercially and over encapsulated using opaque capsules by the UConn Health Research Pharmacy Service. Pbo will be formulated to match the active medication. Subjects will take one 0.5 mg capsule of dutasteride or matching pbo during the first

treatment visit (baseline study visit 2) and at home on day 2 followed by two capsules daily for either 12 or 24 weeks (depending on treatment response). Similarly, subjects transitioning from placebo or dutasteride based on phase 1 non-response will be given one capsule of medication (dutasteride 0.5 mg or naltrexone 25 mg) during their first phase 2 study visit and day 2 of phase 2 followed by two capsules daily for 12 weeks.

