- 2.C.3.d. Medication Randomization and Drug Accountability: Urn randomization (Stout, Wirtz et al. 1994) will be used to assign subjects 1:1 to dutasteride or pbo for treatment phase 1, balancing for number of DSM5 AUD criteria (2-5 vs.>5), DTC relative to total motives score (0-25% vs. >25%), *FKBP5* genotype (CC vs. T-carrier), current smoking status, and use of medication for treatment of co-morbid psychiatric condition. Separate

randomizations will be done for women and men to ensure balance on these variables in both sex groups. At the end of phase 1, patients who have reduced drinks/week by at least 60% will continue for the second 12 wks on the originally randomized treatment taking 2 capsules per day. Subjects who have reduced drinks/wk by less than 60%, will be informed that they will be transitioning to an active study medication (either dutasteride or naltrexone), and will be interviewed to confirm they have not used opioid medication for 5 days prior which will be verified by urine testing, subjects testing positive for opioids will not be eligible for starting phase 2. For non-responder subjects in the phase 1 pbo arm, the pharmacy will begin dispensing 0.5 mg dutasteride capsules with instructions to take 1 capsule per day for 2 days, then 2 capsules daily for 12 weeks. For subjects in the initial dutasteride arm and reducing less than 60%, the pharmacy will dispense 25 mg naltrexone capsules with the same instructions of 1 capsule for days 1 and 2 followed by 2 capsules each day (50 mg naltrexone per day) to match the dutasteride capsule dosing. Medication vials including any unused medication will brought to each follow-up visit. Unused pill counts will be recorded by the study nurse at each bi-weekly visit and medication use recorded daily by patients on their drink log.

2.C.4. Study Visits:

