For the phase 1 comparison of dutasteride and pbo over time, efficacy analyses will be performed using generalized linear mixed (GLMM) models implemented in SPSS. GLMM incorporates within subject correlation effects important in examination of repeated measures, can incorporate multiple covariates, interactions, random and fixed effects, nonnormal distributions, and is often recommended for designs such as proposed (Mallinckrodt C 2017). Medication group will be treated as a factor and treatment week as a continuous covariate. Sex, smoking status, treatment goal (stop vs. reduce drinking), and use of concurrent medication for co-morbid psychiatric conditions will also be examined as baseline between-subject covariates. Medication group, week, and the other covariates will be modeled as fixed effects, and the intercept will be modeled as random effects. For the outcome HDD/wk a binomial distribution with logit link will be used where the number of HDD during the week will be the numerator and number of observed days the denominator. For the outcome SD/wk a negative binomial distribution with log link will be used. An interaction term between medication group and the week term(s) will be used to evaluate whether the efficacy of dutasteride compared to pbo in reducing drinking varies over time. Interaction effects of sex and treatment condition will also be examined. Pretreatment drinking will be controlled using baseline TLFB drinking data as a covariate. The robustness of results will be evaluated by running the model under three different conditions: 1) modified intention to treat using all available outcome information from subjects with at least 1 post-randomization visit, 2) data from 12-week per protocol completers, and 3) multiple imputation using 10 imputed data sets with weekly drinking and baseline covariates thought predictive of the outcomes or missingness included in the imputation phase.

For aim 2, phase 2 outcomes, the within-subjects analysis will compare drinking during phase 1 against phase 2 for three groups: a) patients responsive to dutasteride in phase 1 and continuing on dutasteride for an additional 12-weeks in phase 2, to examine whether the response is maintained with continued treatment; b) phase 1 non-responders crossed over from pbo in phase 1 to dutasteride in phase 2 to provide a second contrast using an A-B design of the efficacy of dutasteride compared with pbo; and c) phase 1

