2.C.9.b. Sample size considerations: For Aim 1, the proposed sample size of 160 completing the phase 1 12-week treatment (80 per arm), has 80% power to show statistical significance (α =0.05) for medium-size effects, d=0.4, such as observed in our initial RCT of dutasteride in men (d=0.38 for change in SDs/wk from baseline to last month of treatment comparing dutasteride and pbo n=91]. For Aim 2a, assuming 80% power and α =0.05 and a sample of 40 responder subjects continuing on dutasteride, the non-inferior margin limit would be an increase of 0.67 HDD/wk or 5 SDs/wk during the second 12 weeks dutasteride treatment. For Aim 2b, a sample of 64 placebo non-responders crossing over to dutasteride for phase 2 would have 90% power to detect a medium effect size for reduction in drinking in phase 2 using a within-subjects t-test. For Aim 3, using the GLMPOWER procedure and the between cell effects for the preliminary data presented above (section 2.B.2) for the 2-way interaction of drinking to cope x drug, a sample of 160 subjects in phase 1 would have 80% power to detect the magnitude of this interaction seen in the preliminary dataset.

Table 3. Timeline for recruitment and other study objectives:

Dutasteride AUD#2 protocok V9 (05-18-2022)

IRB NUMBER: 19-147-2 IRB APPROVAL DATE: 02/27/2024

Staff training & study prep										
Patient enrollment & randomizing 5/mo										
3- and 6-month follow-up										
Data entry & cleaning										
Data analysis & Report writing										

Section 3. PROTECTION OF HUMAN SUBJECTS

3.A Risks to Human Subjects

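### The phase 1 efficacy model names no deciding term, time point or week coding, although Aim 1 is sized on a last-month difference that neither model coefficient, as described, is stated to test

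*Combined protocol and SAP*

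**What the plan says.** Section 2.C.9.a.2 (Efficacy) makes heavy drinking days per week (HDD/wk) and standard drinks per week (SD/wk) the primary outcomes and gives no time point for either. The phase 1 model is a generalized linear mixed model with a random intercept: binomial with logit link for HDD/wk, negative binomial with log link for SD/wk. On its structure the section says "Medication group will be treated as a factor and treatment week as a continuous covariate". A medication-by-week interaction is added to examine whether efficacy changes over time. Baseline drinking is a covariate. The coding of week is not given, and no coefficient or contrast is named as the efficacy test. Table 1 adds only that the arms are compared by GLMM.

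Section 2.C.9.b (Sample size considerations) states that 160 completers, 80 per arm, "has 80% power to show statistical significance (α =0.05) for medium-size effects, d=0.4". The supporting estimate is "d=0.38 for change in SDs/wk from baseline to last month of treatment comparing dutasteride and pbo n=91".

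A last-4-weeks window appears elsewhere: in the definition of phase 1 response, in two secondary outcomes, and in the restricted-period analysis for Aim 2. The primary phase 1 comparison does not use it.

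**The concern.** The trial is sized on a last-month difference, and no test of that difference is specified. With medication, week and their interaction in one model, at least two coefficients could be reported as the efficacy result, and they answer different questions. If week is uncentred and starts at zero, the medication coefficient is the arm difference at week 0. The interaction asks only whether the arms diverge at a steady rate.

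The preliminary-studies section (2.B.2) shows that this freedom has been used. In the whole sample of the prior trial, efficacy was read from treatment-by-time interactions. In the high drinking-to-cope subgroup it was read from the interaction for HDD/wk and from the medication main effect for SD/wk. In the high-anxiety subgroup it was read from a main effect for both outcomes.

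The plan recognises the mechanism for Aim 2. It adds the last-4-weeks analysis there because a slow start would weaken the phase and interaction terms. At stake are the type I error, if the term is chosen after the data are seen, and power, if the term that happens to be reported does not suit the time course.

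**Working it through.** **1. The plan's own figure.** Inputs from 2.C.9.b: 80 per arm, d=0.4, α=0.05, sidedness not stated. The noncentrality is 0.4 × √(80/2) = 2.530.

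- Two-sided: Φ(2.530 − 1.960) = 71.6%.
- One-sided: Φ(2.530 − 1.645) = 81.2%.
- Two-sided with all 95 randomized per arm: 0.4 × √(95/2) = 2.757, giving 78.7%.
- Two-sided at d=0.38, 80 per arm: 67.1%.

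At 80 per arm, the stated 80% is reproduced only by a one-sided test.

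**2. What each coefficient measures.** With week centred at c, the arm difference at week w on the link scale is β_M + β_MW(w − c). Averaged over weeks 9-12 (mean week 10.5) it is β_M + β_MW(10.5 − c). If c=0, β_M is the week-0 difference and the last-month difference is β_M + 10.5β_MW. Only c=10.5 makes β_M the model's last-month difference.

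**3. Power by term.** The documents give neither the weekly correlation ρ nor the time course, so both are assumed. Set-up: weeks 1-12, random intercept, weekly variance 1, Gaussian outcome, two-sided 0.05, 80 per arm. The effect is scaled so that the weeks 9-12 mean difference is 0.4 SD of that mean. Example at ρ=0.5:

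- SD of the weeks 9-12 mean: √(0.5 + 0.5/4) = 0.791, so the difference is 0.4 × 0.791 = 0.316.
- Sum of squares of week about 6.5: 143.
- Interaction, linear effect: slope 0.316/10.5 = 0.0301; SE = √(0.025 × 0.5/143) = 0.00935; z = 3.22; power 89.6%.
- Medication term at week 0, constant effect: SE = √(0.025 × [0.5 + 0.5(1/12 + 6.5²/143)]) = 0.131; z = 2.41; power 67.3%.
- Line read at week 10.5, either effect: SE = √(0.025 × [0.5 + 0.5(1/12 + 4²/143)]) = 0.122; z = 2.59; power 73.5%.

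Ranges over ρ = 0.3-0.7 with a random intercept only:

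| True effect | Medication term (week 0) | Interaction | Line at week 10.5 |
|---|---|---|---|
| Linear from zero | 5% | 66-99.6% | 73-75% |
| Constant | 64-70% | 5% | 73-75% |
| Rises to week 4, then flat | 24-27% | 24-69% | 79-81% |
| Starts after week 4 | 12-13% | 86-100% | 68-71% |

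With random slopes added (intercept SD 1, residual SD 0.8, slope SD 0.03-0.10), the linear case gives 5%, 85-96% and 72-73%. The constant case gives 72-93%, 5% and 72-73%. A comparison of observed weeks 9-12 means has 71.6% in every row.

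**4. Centring at mid-phase (6.5).** In the second set-up, with slope SD 0-0.10, the medication term has 38-49% power under linear growth.

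**5. Type I error if either term may be claimed.** At ρ=0.5 the two uncentred estimates correlate at −0.46, and the chance that at least one is significant under no effect is 9.2%. Over ρ = 0.3-0.7 it is 8.7-9.5%. If the estimates are uncorrelated, as with mid-phase centring and a random intercept only, it is 1 − 0.95² = 9.75%. These figures are per outcome.

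**6. Is a straight line at week 10.5 enough?** Take an effect of 0.25, 0.50 and 0.75 in weeks 1-3 and 1 from week 4. Its mean is 10.5/12 = 0.875. The fitted slope is (5.5×0.75 + 4.5×0.5 + 3.5×0.25)/143 = 7.25/143 = 0.0507. At week 10.5 the line gives 0.875 + 4 × 0.0507 = 1.078 against a true value of 1, an overstatement of about 8%. The 79-81% in the plateau row is inflated by this.

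**The case against.** The plan gives the interaction a descriptive role, which could be taken to make the medication term the efficacy test. It also refers to the week term in a form that allows more than one. Both readings are open. But the plan does not state either, and the prior trial took its main result from the interaction.

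A reader might infer that the medication term is the week-0 difference as a matter of fact. The documents do not support that, because the coding is not stated. The 5% for that term needs both uncentred week and an effect that is exactly zero at week 0.

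A reader might also conclude that power swings from 5% to over 90%. That is not a property of the plan. Each 5% is a limiting case in which the tested coefficient is truly zero. In the random-intercept set-up with a linear effect, the interaction passes 90% only above a weekly correlation of about 0.50. The calculation also approximates logit and negative binomial models by a Gaussian one.

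A third tempting inference is that the pharmacology predicts a plateau in drinking. Section 2.C.3.a expects 60% "inhibition of type 1 5AR by 4 weeks for a total reduction in DHT" of about 80%, with more than 90% inhibition for type II. That is not near-complete inhibition of both enzymes, and nothing there says drinking levels off when inhibition does. The prior trial's treatment-by-time interactions (p=0.002 and p=0.028), and the further decline over time on dutasteride, point toward divergence. That favours the interaction test.

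Finally, the steadiness of the weeks 9-12 contrast is partly built in, since every scenario is scaled to d=0.4 in those weeks. That is also the quantity the sponsor chose for sizing the trial, so the comparison is relevant, but it does not show that this contrast is most powerful.

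**Conclusion.** The gap stands: the plan has no named efficacy term or contrast, no primary time point and no week coding, while Aim 1 is sized on a last-month difference that no stated test addresses. Leaving the choice between the two terms open costs roughly 9% type I error per outcome instead of 5%. This result depends little on the assumed covariance.

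The power consequences are conditional on the assumed trajectories and covariance. Across the trajectories tried, the weeks 9-12 contrast stays at about 68-81%, while the uncentred medication term and the interaction each fall to 5% in one limiting case and do well in another. These figures show sensitivity to the unstated choice; they do not predict this trial's power. The documents do not establish which trajectory will hold.

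**What to change.** Add to 2.C.9.a.2, before treatment codes are opened:

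- For each primary outcome, the single efficacy test is the model-based dutasteride minus placebo difference averaged over weeks 9-12, on the link scale.
- Week enters as categorical, or through a flexible term, so that the contrast does not rest on a straight line.
- The coding of week is stated.
- The medication-by-week term describes time course and is not an efficacy test.

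In 2.C.9.b, tie the Aim 1 power to this contrast and state sidedness: about 72% two-sided with 80 per arm at d=0.4, or 79% if all 95 per arm contribute. Two-sided 80% power would need 2 × (1.960 + 0.842)²/0.4² = 98.1, so 99 per arm.

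The cost is a few sentences and one contrast statement, with no new data or patients. Categorical week adds parameters to the model. The real downside is lower power than the interaction test if the effect grows linearly, as the prior trial suggests it may: in the ρ=0.5 example, about 72-74% against 90%.

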Drinking outcomes. Comparison of treatment groups for the modified intention to treat sample (N=135) on the primary outcomes of HDD/week and drinks/ week using generalized linear mixed models (GLMM) showed significant treatment x time interactions (HDD F=9.2; df=1,1406, p=0.002 and SD/wk F=4.8, df=1,1406, p= 0.028). While a minority of our subjects smoke, in view of prior reports of differential medication effects among smokers vs. non-smokers for naltrexone we examined GLMM models that included smoking status, treatment condition, treatment x time, and treatment x smoking as predictors, and identified significant 2-way interactions of treatment x time (F=9.1, df=1,1404, p=0.003 and F=4.4, df=1,1403, p=0.035 for HDD and SD/wk, respectively), and treatment x smoking (F=8.4, df=1,1404, p=0.004 and F=10.9, df=1,1403, p=0.001 for HDD and SD/wk, respectively), such that smokers (n=12) treated with dutasteride drank more throughout the treatment period than smokers treated with pbo (n=12), while the opposite response was observed for non-smokers (dutasteride=56; pbo=55). Smokers and nonsmokers did not differ on baseline drinking, age, Spielberger State Anxiety (SAI) or Beck Depression Inventory (BDI) scores. The interaction of drug x smoking status may relate to the induction by tobacco of phase I metabolism cytochrome P450 and aldo-keto reductase enzymes (Nagaraj, Beckers et al. 2006), the latter of which are involved in neuroactive steroid biosynthesis and metabolism. A prior study showed a positive correlation between serum cotinine levels and the neuroactive steroid allopregnanolone in a sample of 28 men (Marx, Trost et al. 2006). Somewhat surprisingly, with limited exceptions (Fucito, Park et al. 2012, Litten, Ryan et al. 2013, Schacht, Randall et al. 2017) reports for recent RCTs for AUD either did not report the proportion of smokers (Johnson, Ait-Daoud et al. 2003, Johnson, Rosenthal et al. 2007, Johnson, Ait-Daoud et al. 2011, Johnson, Seneviratne et al. 2013, Kranzler, [name] et al. 2014) or did not include smoking status in the analysis of outcomes (Anton, O'Malley et al. 2006, Anton, Myrick et al. 2011, Fertig, Ryan et al. 2012, Litten, Fertig et al. 2012). Interestingly, in the reports by Fucito et al. (Fucito, Park et al. 2012) and Schacht et al. (Schacht, Randall et al. 2017) naltrexone only benefited drinkers who also smoked while our results with dutasteride indicated only non-smokers were responsive, presumably reflecting distinct mechanisms of change. We will include smokers in the proposed study to further evaluate our initial findings. Dutasteride nonresponsive smokers in phase 1 may experience treatment responsive to naltrexone in phase 2 of the proposed study which would support use of smoking as a factor in individualized treatment recommendations.

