comparison in phase 1 and a within-subjects test in phase 2 for patients treated with pbo in phase 1 and dutasteride in phase 2, iii) allow evaluation of whether reductions in drinking are maintained with ongoing treatment for phase 1 dutasteride responders, and iv) provide preliminary data on whether dutasteride non-responders show reductions in drinking when crossed over to naltrexone, an established medication for AUD with a different mechanism of action compared with dutasteride.

Three and six-month follow-up visits following the completion of the 24-week treatment phase will evaluate the durability of treatment effects, allow measurement of the degree to which dutasteride effects on 5AR inhibition have been reversed following 12- or 24-week exposures and to maintain contact with female participants to remind them of the importance of effective contraception for 6 months following treatment.

Table 1. Expected Patient Distribution for Phase 1 and 2.

Phase 1	Phase 1	Phase 1	Phase 2	Phase 2 Statistical contrasts
Treatment	Statistical	Expected Tx	Treatment	
	contrasts	response groups		
Dutasteride n=95 (grp A)	Between-subject contrasts using GLMM Dut vs. Pbo for DVs HDD/wk and SD/wk;.	Dut-R (wk 9-12 Response n=40) Dut-NR (wk 9- 12 Non-Response n=40)	Dut-R dutasteride Dut-NR naltrexone	Within-subject interrupted time series regression using mixed models. Dut-R: Is dut response maintained? Dut-NR: Do dut NRs respond to naltrexone?
	Moderating			
Pbo n=95 (grp B)	effects of genotype, baseline state vs. trait anxiety, perceived stress and interaction with FKBP5 genotype	Pbo-R (wk 9-12 Response n=16) Pbo-NR (wk 9- 12 Non-Response n=64)	Pbo-R pbo Pbo-NR dutasteride	Pbo-R: insufficient sample for statistical comparison. Pbo-NR: Do pbo NRs respond to Dut?

Phase 1 response ≥ 60% reduction SD/wk for wk 9-12 vs baseline (current study 49% response rate for dut vs. 20% pbo). dutasteride 1 mg/day; naltrexone 50 mg/day.

2.C.2. Patients: Drinkers who want to reduce or stop drinking will be recruited using advertisements in radio and print media, by posting/distributing recruitment materials in community settings, informational mailings to area clinicians and by referral from UConn Health medical and dental clinics in at our main campus in Farmington CT together with

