dutasteride arm non-responders switched to naltrexone to determine whether naltrexone is effective in reducing drinking in dutasteride non-responders. An interrupted time series regression using mixed models will be used (Wagner, Soumerai et al. 2002, mallinckrodt and Lipkovich 2017), where in addition to a variable for week an indicator variable for phase, a second weekly variable that is sequentially coded beginning at phase 2 and the interaction of the two variables will be included in the model. The phase indicator variable will measure change when entering phase 2 and the second weekly variable will measure change in trajectory deviating from phase 1. In addition, a restricted period analysis focusing on the average of the last 4 weeks of phase 1 compared to average of the last 4 weeks of phase 2 will be conducted. This may be more sensitive if the first few weeks of each phase show limited initial response, which would dilute the effects for phase and the interaction for the interrupted regression model. For the first group, dutasteride responders, a non-inferiority test will be used where the non-inferior margin will be 20% above the drinking levels during phase 1. For the latter two groups of non-responders a superiority test will be used.

For aim 3, analysis of drinking outcomes will be repeated including baseline measures of DTC, trait anxiety, perceived stress, adverse child event count and genotype for the *FKBP5* rs1360780 SNP (CC vs. T-carrier) as additional between-subject factors together with the 2- and 3-way interactions of medication condition with DTC, SAI, PSS or ACES measures and *FKBP5* genotype. We will include both Blacks and Caucasians in the pharmacogenetics analysis as our prior study showed similar interactions of *FKBP5* genotype with life stress on drinking measures in both Black and Caucasian college students (Lieberman, Armeli et al. 2016).

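### Smokers are enrolled partly to re-evaluate a prior treatment-by-smoking interaction, but no planned analysis specifies a medication-by-smoking term; as a minor point, the Aim 1 model omits three of the six randomisation factors

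*Combined protocol and SAP*

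**What the plan says.** **Rationale.** Section 2.B.2 (Drinking outcomes) describes prior-trial "GLMM models that included smoking status, treatment condition, treatment x time, and treatment x smoking as predictors". It reports "treatment x smoking (F=8.4, df=1,1404, p=0.004 and F=10.9, df=1,1403, p=0.001 for HDD and SD/wk, respectively". The non-smokers (56 dutasteride, 55 placebo) and the smokers went in opposite directions, "such that smokers (n=12) treated with dutasteride drank more throughout the treatment period than smokers treated with pbo (n=12". The section then states: "We will include smokers in the proposed study to further evaluate our initial findings". It adds that a naltrexone response among smokers who had not responded to dutasteride would support using smoking to guide individual treatment recommendations.

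**Randomisation.** Section 2.C.3.d uses five urn factors (AUD criteria count, DTC share of motives, FKBP5 genotype, current smoking, psychiatric medication) and randomises women and men separately. That makes six factors.

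**Analysis.** For Aim 1, section 2.C.9.a.2 says: "Sex, smoking status, treatment goal (stop vs. reduce drinking), and use of concurrent medication for co-morbid psychiatric conditions will also be examined" as baseline covariates, alongside baseline drinking. It includes medication by week and adds: "Interaction effects of sex and treatment condition will also be examined". Aim 3 adds the "2- and 3-way interactions of medication condition with DTC, SAI, PSS or ACES measures" and FKBP5 genotype. Table 1 lists as moderators the "effects of genotype, baseline state vs. trait anxiety, perceived stress and interaction with" FKBP5. The phase 2 models name no smoking term.

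**The concern.** The plan gives a scientific reason for enrolling smokers and balances the arms on smoking, but does not commit to the contrast that would address that reason. A smoking main effect says whether smokers drink more or less overall. It does not say whether dutasteride works differently in them. If the contrast is run later, readers will see an unplanned subgroup result, which is harder to interpret than the same estimate named in advance.

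Separately, AUD criteria count appears in no named model, and DTC and FKBP5 enter only when the analysis is repeated for Aim 3. Omitting factors on which the arms were balanced leaves their variance in the error term, so the medication main-effect test is slightly conservative.

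**Working it through.** **1. Which analysis contains the term?**

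| Analysis | Role of smoking | Medication interactions named |
|---|---|---|
| Prior trial (2.B.2) | main effect and interaction | time, smoking |
| Aim 1 (2.C.9.a.2) | covariate | week, sex |
| Aim 2, phase 2 | not named | none by baseline factor |
| Aim 3 and Table 1 | not named as moderator | DTC, anxiety, perceived stress, ACES, FKBP5 |

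Sex is in the same covariate sentence as smoking, yet receives its own interaction sentence. Smoking does not. The natural reading is that smoking is planned as a main effect only.

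**2. Published figures.** F=8.4 on 1 and 1404 df gives p=0.0038; F=10.9 on 1 and 1403 df gives p=0.0010. Both match section 2.B.2. The 80% power in section 2.C.9.b (80 per arm, d=0.4, α=0.05, sidedness not stated) reproduces one-sided at 80.9%; two-sided it is 71.0%.

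**3. Precision of the missing contrast.** Inputs: smoker share 24/135 = 17.8% (assumed to carry over); modified intention-to-treat size 190 × 135/142 ≈ 181 (prior-trial retention assumed). Smokers: 181 × 0.178 ≈ 32.2; non-smokers ≈ 148.8. In outcome SD units, with 1:1 allocation within each group:

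- SE = √(4/32.2 + 4/148.8) = 0.389. The 95% half-width is 1.97 × 0.389 ≈ 0.77.
- Within smokers: 1.97 × √(4/32.2) ≈ 0.70. Within non-smokers: 1.97 × √(4/148.8) ≈ 0.32.
- At 10% smokers: SE = √(4/18.1 + 4/162.9) = 0.496, half-width about 0.98. At 25%: SE = √(4/45.25 + 4/135.75) = 0.343, half-width about 0.68.
- In 160 completers at 17.8%: SE = √(4/28.4 + 4/131.6) = 0.414.

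**4. Power if the prior interaction is taken at face value.** Prior SE = √(1/12 + 1/12 + 1/56 + 1/55) = 0.450. The implied interaction is √8.4 × 0.450 = 1.30 SD for heavy drinking days (HDD) and √10.9 × 0.450 = 1.49 SD for standard drinks per week (SD/wk). Two-sided power at 0.05, noncentral t:

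| Patients, smoker share | Full effect (HDD / SD/wk) | Half effect (HDD / SD/wk) |
|---|---|---|
| 181, 17.8% | 92% / 97% | 39% / 48% |
| 181, 10% | 75% / 85% | 26% / 32% |
| 181, 25% | 97% / 99% | 47% / 58% |
| 160, 17.8% | 88% / 95% | 35% / 43% |

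These are linear approximations to logit and negative binomial mixed models. The implied SDs are rough, because the prior F tests used repeated-measures degrees of freedom. With 12 smokers per arm the prior effect may be overstated.

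**5. Phase 2.** Of the 40 expected dutasteride non-responders, 40 × 0.178 ≈ 7 would be smokers. The ceiling, if every smoker in the 80 dutasteride completers failed to respond, is 80 × 0.178 ≈ 14.

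**6. Omitted randomisation factors.** If the three factors explain a share R² of the variance (no figure in the documents; 3-10% assumed), including them raises the effective d to 0.4/√(1−R²). At 80 per arm, two-sided power goes from 71.0% to 72.3% (R² = 3%), 73.2% (5%) or 75.5% (10%), a gain of 1.3 to 4.5 points. With the factors omitted but balanced, type I error for the medication main effect is about 2 × [1 − Φ(1.96/√(1−R²))]: 0.044 at R² = 5% and 0.039 at 10%.

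**The case against.** The strongest reply is that the plan is loosely worded rather than closed. It says smoking will be examined, in a model class described as able to carry interactions; smoking is recorded and balanced, so the contrast stays estimable; and it belongs to no Specific Aim. Much of this stands. A reader might infer that both the model and the analysis set would have to be invented after the data are seen. The documents do not support that: section 2.B.2 shows a fitted model form, and section 2.C.9.a.2 names three analysis sets. What does not stand is reading an interaction into the covariate sentence, given the separate sentence for sex.

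On covariates, nothing commits the plan to adjust for every balancing factor, two of the three do appear under Aim 3, and the error is conservative. That is why it is only a minor point.

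A reader might also infer that enrolling smokers dilutes the planning effect of d=0.38 and so weakens the primary test. Section 2.C.9.b does not say that its 91 patients were non-smokers. The same count appears in the non-smoker paragraph of section 2.B.2, which makes this an inference. In any case it is a sample-size question: a smoking interaction would not restore pooled power.

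**Conclusion.** The gap is real and limited. No planned analysis specifies medication by smoking, although the protocol gives that question as its reason for including smokers. It is a secondary question, and what is lacking is an explicit commitment. The estimate would be imprecise: a half-width of about 0.77 SD at 181 patients, or 0.68 to 0.98 SD for 25% to 10% smokers, resting on the prior trial's smoker share and retention and on a linear approximation. A reader might expect the added term to confirm or refute the prior finding. It cannot be relied on for that, since power falls to 39-48% if the true interaction is half the prior one.

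The covariate omission costs roughly 1 to 4.5 power points two-sided under an assumed R² of 3-10%, and leaves medication by week essentially unaffected.

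**What to change.** 1. Add medication by smoking as a prespecified secondary interaction in the modified intention-to-treat set for both primary outcomes, in the form fitted in the prior trial. Report dutasteride-placebo odds ratios (HDD) and rate ratios (SD/wk) with 95% confidence intervals for smokers and non-smokers, beside the pooled estimate. State that it is for estimation, give the expected precision, and say that a week-averaged contrast does not show whether the medication-by-week trajectory differs by smoking.
2. Enter all six randomisation factors in the Aim 1 model, in their randomisation categories, with baseline drinking and treatment goal. Reword Aim 3 so that it adds the DTC and FKBP5 interactions (and the DTC score, if used) to that model, since those factors would no longer be additional.
3. Report phase 2 change on naltrexone by smoking status descriptively only.

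The cost is analysis-plan wording; every variable is already collected by randomisation. The downside is three more covariate degrees of freedom and one imprecise interaction that must not be over-read.
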